5.3 TRIAL-SPECIFIC SCREENING TESTS

Participants will undergo serological testing (e.g. TB ELISpot) to check for latent TB, as detailed in the adalimumab SmPC. Participants will also undergo serological testing for hepatitis B surface antigen as detailed in the adalimumab SmPC. Approximately 10ml of blood will be taken from each participant for these tests. These tests are to be carried out locally therefore the samples will be processed within 72 hours at the local site lab and any remaining should be destroyed in compliance with HTA and local procedures.

These tests will be performed at the time the patient attends for their first injection appointment. The risks of reactivation of TB are well-documented only in patients who receive anti-TNF therapy on a regular basis e.g. every 2 weeks for adalimumab, in the long term. Discussions with [name], former head of the Oxford TB service, indicated that the risk of TB reactivation following a single injection are low and any participant for whom the serology test result shows them to be TB positive will be referred for a chest X-ray and to the local TB service and will not receive any further trial treatment; they will still be included in the 3 month follow up assessment as specified in the protocol. Similarly, the risk of reactivation of latent hepatitis B after a single injection of adalimumab is very low and any participant that test positive for hepatitis B surface antigen will be referred to their local infectious disease service. They will be recorded as withdrawn from treatment but will continue to be followed up at the 3 month time point.

Participants who do not meet the eligibility criteria or who do not wish to participate will receive the standard NHS treatment. We will record anonymised information on the age and sex of those who

decline to participate so that we can assess the generalisability of those screened. The reasons for declining will be asked and any answers given will be recorded.

5.4 CODE BREAK

Based on the well-known safety profile of the IMP, it is not anticipated that there will be any suspected unexpected serious adverse reactions. In the event that the participant has a serious adverse reaction within 3 months of the last injection and there is a need to unblind for emergency purposes the PI at site will have 24/7 access to the randomisation database (RRAMP) and can access the treatment allocation for that one participant without delay. The CTU will be notified immediately that an unblinding has occurred.

All participants will be provided with a laminated card to present to any treating physicians with outline details of the trial treatment as well as contact details of the site in the event of unblinding.

5.5. SAMPLE SIZE

The main feasibility objective and therefore the basis of the sample size estimate is participant recruitment at least 5 centres with a staggered start. The target sample size is 84 participants, equivalent of 1 to 2 participants per month per site over 12 months, allowing for staggered opening of sites. Seventy is the recommended minimum target sample size when including an estimate of the SD in an external pilot trial (48). The sample size has been increased from 70 to a total of 84 participants in order to increase precision of the estimate of the standard deviation of SPADI at 3 months, the proposed primary outcome for the definitive trial, and to take into account possible attrition (based on an attrition rate of 15%). This attrition rate is a conservative estimate based on attrition rates for the GRASP trial (14% at 6 months) (32) and UK FroST (11% at 3 months) (12) which represent similar populations to those anticipated in Anti-FREAZE. This sample size will enable an estimate of a participation rate of 30% with a precision of +/- 5% based on 280 eligible participants being identified. We have selected a conservative recruitment rate given the uncertainty around the ability to identify, recruit and inject participants with early stage frozen shoulder. We anticipate that we will be able to recruit the required number of participants over a 12 month period. See Section 6.4 for details related to the sample size for the embedded qualitative sub-study.

6. METHODS - DATA COLLECTION, MANAGEMENT AND ANALYSIS

6.1. DATA COLLECTION METHODS

6.1.1. Baseline data collection

After the participants have been assessed for eligibility and informed consent has been obtained, participants will be asked to complete a baseline assessment questionnaire that will record simple demographic information and baseline measurements for the primary and secondary outcomes, shown in Table 3. The questionnaires will be available in both an online and paper format as, due to their frozen shoulder, participants may find one format much easier to complete than the other.

Table 3: Outcomes and time points of assessment

Outcome	Measurement	Time point
Demographic	Age, Sex, Height, Weight, Ethnicity, Smoking, Date of frozen shoulder diagnosis, Duration of symptoms, Hand dominance, Affected shoulder. Diabetes and type, Dupuytren's Disease	0
Shoulder range of movement	Clinician assessed (goniometry measured) active shoulder flexion, extension, abduction, internal and external rotation. Patient Reported ROM Questionnaire	0, 3 months
Pain and function	Shoulder Pain and Disability Index (SPADI) (38, 39) 13-item total scale	0, 3 months
Pain	Shoulder Pain and Disability Index (SPADI) (38, 39) 5-item subscale	0, 3 months
Function	Shoulder Pain and Disability Index (SPADI) (38, 39) 8-item subscale	0, 3 months
Psychological factors	Fear Avoidance Belief Questionnaire physical activity 5-item subscale (40) Pain Self-efficacy questionnaire (short form) (41)	0, 3 months
Sleep disturbance	Insomnia Severity Index (42)	0, 3 months
Global impression of treatment	Patient-rated Likert scale (43)	3 months
Return to desired activities	Patient-reported return to desired activities, including work, social life and sport activities (49)	0, 3 months
Health resource use	Consultation with primary and secondary care, additional physiotherapy, injection use, or alternative therapies for index shoulder	3 months
Adverse Events	Any Grade 3 or above AEs that have occurred from Consent up until the 3 month Follow up.	3 months

6.1.2. Follow-up data collection

Follow up will be conducted via face to face clinic assessment and patient reported questionnaire at 3 months after randomisation. Detail of the outcomes to be assessed, how they will be measured and at which time points are shown in Table 3.

Participants who are unable to attend the face to face appointment will be asked to complete the 3 month follow up questionnaire and return it to the Anti-Freaze-F Trial Office in a prepaid envelope (the ROM participant Questionnaire can only be completed on paper, these will be supplied to the site to send out to participants if needed) or online (web-based version of the questionnaire) as appropriate. The reason why a participant is unable to attend the face to face clinic appointment will be recorded and whether this was due to potential COVID-19 restrictions or due to other reasons. For those who do not respond to the initial 3 month follow up questionnaire a reminder questionnaire will be sent 2 weeks later. Telephone and email follow-up will be used (2 weeks later) to contact those who do not respond to either the initial or reminder questionnaire. For those participants who have requested for digital communication, the ROM will need to be sent to them via the post in paper format. These participants will be send digital reminders if we do not receive the ROM questionnaire back at the trial office. Telephone and email follow-up will also be used to collect a core set of questionnaire items for the Shoulder Pain and Disability Index (SPADI) (primary outcome) if these have not been fully completed on the returned questionnaire.

6.1.3. Discontinuation / withdrawal of participants

Participants will be informed that they have the right to withdraw from the Anti-Freaze-F trial at any time without having to provide a reason and with no impact on their future health care. A participant may wish to discontinue their treatment and/or withdraw from follow-up data collection. If a participant wishes to discontinue their treatment, the study team will contact the participant and ask if they are still willing to participate in the collection of follow-up data. Participants that continue to participate in follow-up data collection will not be considered a withdrawal in accordance with the principles of the intention to treat (ITT) analysis. If a participant wishes to withdraw from follow-up data collection, data collected up to the point of withdrawal will still be used, as detailed in the PIL. Results from the blood samples taken will still be used. These will have been destroyed by the local laboratory once the samples have been tested for Hepatitis B/TB. If a participant decides to withdraw before they are given the injection but after the blood sample has been taken, the sample will be destroyed within 72 hours in accordance with HTA and local procedures.

In addition to participant self-withdrawal, an investigator may decide to withdraw a participant from Anti-Freaze-F if considered necessary for any reason including ineligibility arising subsequent to their initial enrolment in the trial or for clinical reasons based on safety grounds (i.e. any relate grade 3 or above Adverse Event as per the Common Terminology Criteria for Adverse Events (CTCAE) v5.0 (see Section 7.2) or tests positive for TB or hepatitis B surface antigen). Participants will still be included in the 3-month follow up assessment. The reason for withdrawal (if given) will be recorded on the study CRFs.

6.2. DATA MANAGEMENT

All data will be processed according to the UK General Data Protection Regulations (GDPR) and the Data Protection Act 2018. All documents will be stored safely in confidential conditions. A data management and sharing plan will be produced for the trial and will include reference to confidentiality, access and security arrangements. All trial-specific documents, except for the signed consent form and follow-up contact details, will refer to the participant with a unique study participant number/code and not by name.

Trial data will be collected and managed using REDCap electronic data capture tools hosted at OCTRU, University of Oxford. REDCap (Research Electronic Data Capture) is a secure, web-based application designed to support data capture for research studies, providing 1) an intuitive interface for validated data entry; 2) audit trails for tracking data manipulation and export procedures; 3) automated export procedures for seamless data downloads to common statistical packages; and 4) procedures for importing data from external sources.

Wherever possible, trial data will be entered directly into the trial database by site staff or participants using an electronic tablet provided by the trial, with the questionnaire already opened to complete. Participants and staff should wash their hands or use anti-bacterial gel before handling the tablets to ensure infection control. Data on paper forms or captured during phone calls to participants will be entered into the trial database by suitably trained Trial office staff. Full details will be recorded in the DMP. The participants will be identified by a unique trial specific number in any data extract. Identifiable data will only be accessible by members of the study team with a demonstrated need (managed via access controls within the application) and any additional processing of this will only be for the purposes of communication with the participant (e.g., sending follow-up reminders for online form completion or telephone follow-up).

Data will be collected from participants via eCRFs at screening, baseline and 3 month follow up. Sites will be provided with an electronic tablet to use for data collection and the ROM assessment will be provided in paper format. If the site or participant are not able to complete the CRFs electronically (due to poor internet connection), paper-based CRFs will be available in the Investigator Site File, these will be returned to the central Trial Office in Oxford via post using a pre-addressed stamped envelope, email as appropriate, or via Trial Office staff at site visits. Sites will send copies of consent forms (if completed paper-based) to the Trial Office via secure NHS email, or via recorded delivery. Participant data will be stored and transported in accordance with OCTRU SOPs. Participants who claim reasonable travel expenses will have their financial information held in accordance with the University of Oxford financial policy for 7 Years.

Upon completion of the trial, and with appropriate participant consent, anonymised research data may be shared with other organisations on request to the Chief Investigator and in accordance with the data sharing policies of OCTRU, the Sponsor and funder(s); as detailed in section 8.4 of the protocol (Access to Data). Participant electronic files will be filed in numerical order and stored in a secure and accessible manner on the ANTI-FREAZE F secure eTMF. Trial documentation including data will be archived for a maximum of 5 years. The Investigator Site File and associated documents should be archived in line with local site R&D policies.

6.2.1 Source Data

Source documents are where data are first recorded, and from which participants' CRF data are obtained. These include, but are not limited to, hospital records (from which medical history and previous and concurrent medication may be summarised into the CRF), clinical and office charts, laboratory and pharmacy records, diaries, microfiches, radiographs, and correspondence. CRF entries will be considered source data if the CRF is the site of the original recording (e.g. there is no other written or electronic record of data). All documents will be stored safely in confidential conditions. On all trial-specific documents, other than the signed consent, the participant will be referred to by the trial participant number/code, not by name.

The following data are expected to be recorded directly on the CRFs hence are to be considered source documents:

- All participant completed questionnaires.

6.3. STATISTICAL METHODS

Feasibility outcomes will be reported, including the number of participants approached, those eligible, consenting to randomisation and follow-up, the delivery of intervention (including time to first injection), withdrawal rate, the number receiving a second injection (per group and overall) and data completeness. Baseline characteristics (including possible stratification factors for the definitive trial) will be reported using descriptive statistics, separately per group and overall using the mean and standard deviation (or median and inter-quartile range if non-normally distributed) for continuous variables and the number and percentage of participants in each group for categorical variables. Measures of central location and dispersion of clinical and patient reported outcome measures, including health resource use, at 3 months will be reported and differences between treatments for the intention-to-treat population (i.e. the population of participants as randomised) will be reported with 95% confidence intervals. The standard deviation of the proposed primary outcome for the larger, main trial, SPADI at 3 months, will be used to inform an estimation of the sample size required for the definitive trial. An estimate of treatment effectiveness will be reported together with its 95% confidence interval. This along with change from baseline in range of shoulder motion at 3 months will provide an indication of potential efficacy of the intervention but will not be powered to provide a definitive result, which will only follow the fully powered definitive main trial. Even small increases in range of shoulder motion are important to people with frozen shoulder, where pain and restricted shoulder movement can be very debilitating. As such, we will use a 10-degree improvement in active flexion with any associated improvement in active external rotation of the shoulder to mean a potentially important difference (50). If we observe this difference between groups in our feasibility study with short follow up and a small sample this would indicate potential efficacy, which should then be formally, tested in the full trial. Adverse events and serious adverse events (S/AEs) will be summarised per group and overall in all patients.

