6.5. PROGRESSION CRITERIA

Progression criteria for the future definitive trial will be judged using a traffic light system whereby 'Green' indicates it is feasible to proceed to a definitive trial with the current procedures, 'Amber' indicates modification to one or more aspect of the study is required before proceeding to the future definitive trial, and 'Red' indicates it is not feasible (53). The decision to progress to a future definitive trial will be made by the Trial Management Group in conjunction with the Trial Steering Committee, based on the criteria in Table 4. It will also be informed by findings from the embedded qualitative study and any potential signal of efficacy due to improvement in range of shoulder motion as a result of anti-TNF injection.

Table 4: Progression criteria

	Green	Amber	Red
Feasibility to recruit: % of potentially eligible patients with frozen shoulder screened across 5	≥33%	≥20% to 32%	<20%

sites in 12 months eligible for recruitment			
Success of consent process: % of eligible participants consented	≥33%	≥20% to 32%	<20%
Intervention delivery: % of participants receive 1 st injection as randomised within specified timeframe	≥75%	≥50% to 74%	<50%

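### Section 6.3 names no model for the 3-month treatment differences and a change score for range of motion; regression on arm, baseline value and centre would usually give narrower intervals from data already recorded

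*Combined protocol and SAP*

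**What the plan says.** Section 6.3 holds the whole quantitative analysis plan. Outcomes at 3 months are summarised and "differences between treatments for the intention-to-treat population (i.e. the population of participants as randomised) will be reported with 95% confidence intervals". An estimate of treatment effectiveness with its 95% interval follows, and then: "This along with change from baseline in range of shoulder motion at 3 months will provide an indication of potential efficacy". Neither this section nor any other names a regression model, a baseline covariate or a centre term.

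The same section attaches a reading rule to range of motion: "we will use a 10-degree improvement in active flexion with any associated improvement in active external rotation of the shoulder" counts as potentially important, and "If we observe this difference between groups in our feasibility study with short follow up and a small sample this would indicate potential efficacy". Under section 6.5 the decision to progress is "based on the criteria in Table 4. It will also be informed by findings from the embedded qualitative study and any potential signal" of efficacy in range of motion.

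The covariates are available. Section 5.1 stratifies randomisation by centre. Section 6.1.1 has participants give "simple demographic information and baseline measurements for the primary and secondary outcomes, shown in Table 3". That table lists, at 0 and 3 months, SPADI and its subscales, goniometry, the patient-reported movement questionnaire, fear avoidance, pain self-efficacy, insomnia and return to desired activities. Global impression and health resource use are collected at 3 months only.

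**The concern.** The sponsor has chosen to report between-arm differences with intervals and to read one of them against a fixed threshold. That reading uses the observed difference, so the precision of the estimator sets how often chance alone reaches 10 degrees.

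A plain 3-month difference ignores the baseline value. A change score uses it with a fixed coefficient of 1, which adds noise when the correlation is moderate. Regression on baseline lets the data set the coefficient, and adding centre respects the way participants were randomised.

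Range of motion may also have fewer completers than SPADI. Goniometry needs the clinic visit, whereas "Participants who are unable to attend the face to face appointment will be asked to complete the 3 month follow up questionnaire" by post or online. At stake are wider intervals than necessary on the continuous outcomes and a somewhat higher chance of a spurious range-of-motion signal.

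**Working it through.** **The plan's own figure.** Section 5.5 starts from 70 participants and allows 15% attrition: 70 / 0.85 = 82.4, so 83, against the stated 84; and 280 × 0.30 = 84. The target is reproduced and is not affected by this point. Expected completers: 84 × 0.85 = 71.4, so 71 (36 and 35 per arm).

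**Assumed inputs.** The documents give no correlation r, no flexion SD and no separate count of range-of-motion completers. I take r = 0.3, 0.5 and 0.7, with 0 and 0.9 to 0.95 as extremes; flexion SD of 20, 25 and 30 degrees; and 50 completers in 10 centres as an unfavourable case. Section 5.5 says at least 5 centres.

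**Standard errors**, with k = √(1/n1 + 1/n2):
- Simple difference: SD × k
- Change score: SD × k × √(2(1 − r))
- Baseline-adjusted: SD × k × √(1 − r²), before the small cost of the extra terms

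In large samples the width ratios to the adjusted analysis are therefore 1/√(1 − r²) for a simple difference (1.05/1.15/1.40) and √(2/(1 + r)) for a change score (1.24/1.15/1.08).

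**With baseline and centre terms paid for.** These are mean interval widths in simulated trials with no centre effect and blocks of 2 or 4 within centre (block sizes assumed).

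| 71 completers, 5 centres | r = 0.3 | r = 0.5 | r = 0.7 |
|---|---|---|---|
| Simple ÷ adjusted | 1.04 | 1.14 | 1.38 |
| Change ÷ adjusted | 1.22 | 1.14 | 1.07 |

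With 50 completers in 10 unequal centres the ratios are about 1.01/1.11/1.35 and 1.19/1.11/1.04.

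**Where adjustment loses.** At r = 0 with no centre effect it is about 1% (71 completers, 5 centres) to 4% (50 completers, 10 centres) wider than a simple difference. It breaks even near r = 0.13 in the first case and about 0.25 in the second. Against a change score it is level, or up to about 2% wider, at r of about 0.9 to 0.95. If centre does explain variance (intraclass correlation 0.05, 71 completers, 5 centres), adjustment is about 1% narrower than a simple difference even at r = 0.

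**Flexion half-width at r = 0.5.** Here √(2(1 − r)) = 1, so the simple difference and the change score coincide.
- 71 completers: k = 0.237 and t(69) = 1.995 give 0.474 SD, that is 9.5/11.8/14.2 degrees at SD 20/25/30. Adjusted, 5 centres, about 0.414 SD: 8.3/10.3/12.4 degrees.
- 50 completers: k = 0.283 and t(48) = 2.011 give 0.569 SD, that is 11.4/14.2/17.1 degrees. Adjusted, 10 centres, about 0.508 SD: 10.2/12.7/15.2 degrees.

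**Chance of a false signal.** The rule is taken as a flexion difference of at least 10 degrees together with an external-rotation difference above 0. I assume no true effect, r = 0.5, 71 completers, and a correlation of 0 to 0.5 between the two differences.

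| Flexion SD | Change score | Adjusted |
|---|---|---|
| 20 | 0.9–1.6% | 0.4–0.7% |
| 25 | 2.3–4.1% | 1.3–2.3% |
| 30 | 4.0–6.8% | 2.6–4.6% |

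The fall is roughly 0.5 to 2.2 percentage points. The adjusted column uses √(1 − r²) without the centre terms, so the true fall is slightly smaller.

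**The case against.** The best case for leaving 6.3 alone has four parts.

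- **The text is silent, not explicitly unadjusted.** This stands. A reader might infer that the sponsor decided against adjustment. The section does not say so for the 3-month differences; only the change score for range of motion is named. What is needed is a statement of the model.
- **Adjustment is not free or always better.** This stands too. A reader might infer that it narrows every interval at no cost. In a trial of this size it spends degrees of freedom and loses a little at very low or very high correlation, as shown above. The loss is small beside the gain at moderate r.
- **The comparison hardly matters.** Section 6.3 declares it not powered, and the primary objectives are feasibility, the SPADI SD and attrition. A reader might infer that a false signal could by itself carry the trial forward. Section 6.5 does not support that: Table 4 has no efficacy criterion, and range of motion only also informs the decision. This limits the importance, but does not explain why the less precise estimator should be preferred.
- **Linear regression may not suit every score, and missing baselines could drop participants.** The first part has little force, since a regression-based difference relies on normality no more than a plain difference in means does. The second is fair and needs a rule.

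**Conclusion.** The point holds as a cheap improvement in precision. The planned comparisons are valid, and nothing in the documents supports calling them biased or the sample size of 84 wrong. At r = 0.5 with 71 completers in 5 centres, either planned method gives an interval about 1.14 times as wide as the adjusted analysis. At r = 0.3 the gain over a simple difference is only about 4%, and at r = 0.7 the gain over a change score is about 7%.

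That no model is stated, and that the covariates are recorded, is certain from the text. The size of the gain is not: it rests on assumed values of r, flexion SD, completer numbers and number of centres.

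**What to change.** In section 6.3, state the following:

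1. For each continuous outcome measured at 0 and 3 months, the treatment difference and 95% interval come from linear regression on arm, the baseline value of that outcome and centre. The movement questionnaire and return to desired activities are included if scored continuously.
2. Small centres are pooled by a rule fixed before outcome data are seen.
3. Participants with a missing baseline value stay in the analysis, for example by mean imputation of the baseline covariate without regard to arm.
4. The 10-degree flexion and external-rotation signal is read from the adjusted differences, with both intervals shown.
5. Global impression and health resource use, which have no baseline value, are reported as now planned.
6. The 3-month SPADI SD is still reported, since it is a primary objective. Beside it go the baseline-to-3-month correlation and the residual SD, so that the definitive trial can be sized for an adjusted analysis if one is chosen.

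The cost is wording and a few degrees of freedom. No new data or participants are needed.

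### Section 6.3 states no baseline adjustment for the 3-month between-group differences, and Section 6.5 takes range of motion but not SPADI into the progression discussion (minor)

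*Combined protocol and SAP*

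**What the plan says.** Section 6.3 states that "differences between treatments for the intention-to-treat population (i.e. the population of participants as randomised) will be reported with 95% confidence intervals". It then promises an estimate of treatment effectiveness with its interval and continues: "This along with change from baseline in range of shoulder motion at 3 months will provide an indication of potential efficacy of the intervention". The same sentence concedes that the result "will not be powered to provide a definitive result".

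For range of motion it sets a benchmark: "we will use a 10-degree improvement in active flexion with any associated improvement in active external rotation of the shoulder". It reads that benchmark as follows: "If we observe this difference between groups in our feasibility study with short follow up and a small sample this would indicate potential efficacy". The sentence then leaves the formal test to the full trial.

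Section 6.5 rests progression on the three feasibility criteria in Table 4. It adds that the decision will also draw on the qualitative findings and on "any potential signal of efficacy due to improvement in range of shoulder motion as a result of anti-TNF injection". SPADI is not mentioned there, although Sections 4.4.2 and 5.5 identify it as the proposed primary outcome of the definitive trial. Table 3 (Section 6.1.1) schedules both SPADI and clinician-measured active range of motion at 0 and 3 months.

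**The concern.** There are two gaps.

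**The estimate is not fixed.** Section 6.3 refers to outcomes at 3 months, to change from baseline, and to a difference between groups. It does not say how the baseline value enters the between-group difference. A 10-degree difference could therefore be a difference in 3-month means, in change scores, or in baseline-adjusted means. On the same data these can fall on different sides of 10 degrees. Without adjustment, precision is also lost in a small trial, although the baseline values will be in hand.

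**The two sections do not match.** Section 6.3 treats the effectiveness estimate and range of motion together as the indication of potential efficacy. The effectiveness sentence does not name its outcome, but it directly follows the one on SPADI. Section 6.5 carries only range of motion forward. Those deciding on progression are thus pointed to a secondary measure and not to the outcome on which the definitive trial would be judged.

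**Working it through.** **Inputs.** From Section 5.5: 84 randomised, 15% attrition. From Table 3: SPADI and active range of motion at 0 and 3 months. Not in the documents, so assumed: flexion SD of 20, 30 or 40 degrees, equal at both visits, and a baseline to 3-month correlation r of 0.5 or 0.7.

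**The plan's own figure.** 70/(1 − 0.15) = 82.4, rounded up to 83, against the stated 84; and 280 × 0.30 = 84. The sample size is not in dispute.

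**Completers.** 84 × 0.85 = 71.4, taken as 35 and 36 per arm. Goniometry needs the clinic visit, while Section 6.1.2 recovers SPADI remotely, so flexion could have fewer. The ratios below do not depend on this number.

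**Standard errors.** With sqrt(1/35 + 1/36) = 0.2374:

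- 3-month means: SE = 0.2374 × SD
- Change scores: that SE × sqrt(2(1 − r)), a factor of 1.00 at r = 0.5 and 0.77 at r = 0.7
- Baseline-adjusted: that SE × sqrt(1 − r²), a factor of 0.87 at r = 0.5 and 0.71 at r = 0.7

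Adjusted against change score, the ratio is sqrt((1 + r)/2): 0.87 at r = 0.5 and 0.92 at r = 0.7. So adjustment narrows the interval by about 13% or 29% against 3-month means, and by about 13% or 8% against change scores.

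**In degrees.** SE, with the 95% half-width (1.96 × SE) in brackets:

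| SD | 3-month means | Change, r = 0.5 | Change, r = 0.7 | Adjusted, r = 0.5 | Adjusted, r = 0.7 |
|---|---|---|---|---|---|
| 20 | 4.75 (9.3) | 4.75 (9.3) | 3.68 (7.2) | 4.11 (8.1) | 3.39 (6.6) |
| 30 | 7.12 (14.0) | 7.12 (14.0) | 5.52 (10.8) | 6.17 (12.1) | 5.09 (10.0) |
| 40 | 9.50 (18.6) | 9.50 (18.6) | 7.35 (14.4) | 8.22 (16.1) | 6.78 (13.3) |

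A t quantile with 35 per arm gives 9.5, 14.3 and 19.1 for the 3-month means, about 2% wider. At SD 30, an observed 10 degrees has an interval of −4.0 to 24.0 from 3-month means, −2.1 to 22.1 adjusted at r = 0.5, and 0.0 to 20.0 adjusted at r = 0.7.

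**How far the candidate estimates can differ.** The difference in 3-month means minus the difference in change scores equals the chance baseline difference between arms. If the baseline SD matches the 3-month SD, that difference has a standard error of 4.75, 7.12 or 9.50 degrees at SD 20, 30 or 40. This is not small beside a 10-degree benchmark. Adjustment accounts for the imbalance and settles in advance which estimate is meant.

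**6.3 against 6.5.** Section 6.3 has two inputs to the efficacy indication; 6.5 has one. Nothing in either section explains why the effectiveness estimate drops out.

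**The case against.** The strongest reply is that 6.3 already does most of what is needed. Intervals are planned for every between-group difference, flexion included. The text calls the sample small, disclaims power, speaks only of potential efficacy and defers to the full trial. All of that stands.

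A reader might infer that the plan misreads a point estimate because the benchmark sentence does not repeat the interval. The documents do not support that. The interval is reported in the same paragraph, and the only stated consequence of a signal is formal testing. Nor is the false-signal risk alarming for a supplementary input: with no true effect, flexion alone reaches 10 degrees in 0.2% to 14.6% of trials across the assumed SDs, unadjusted or adjusted, and the rotation condition lowers that further. A true 10-degree benefit does miss the benchmark half the time on flexion, but so does any threshold set at the true effect, and no consequence is stated for missing it.

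A reader might also infer a faulty go/no-go rule. Table 4 contains no efficacy criterion, and the signal only informs the decision.

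On baseline, it is fair to say that 6.3 points towards a difference in change. That is a legitimate analysis, but it is not stated as the between-group estimate, and adjustment is at least as precise at either assumed correlation. On SPADI, not being named is not being excluded: its difference will be reported, and range of motion taken by a blinded assessor is a defensible supplementary measure. What remains is a mismatch between two sections.

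**Conclusion.** The point holds and is minor. Section 6.3 does not use the collected baseline values to adjust the 3-month differences, and 6.5 leaves out the outcome that 6.3 pairs with range of motion. The size is a standard error multiplied by 0.87 (r = 0.5) or 0.71 (r = 0.7) against 3-month means, and by 0.87 or 0.92 against change scores. These factors rest on assumed correlations and on equal SDs at the two visits. The widths in degrees rest further on an assumed flexion SD and about 71 completers. The sample size, the Table 4 criteria and the 10-degree benchmark are unaffected.

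**What to change.** In Section 6.3, keep the 10-degree benchmark with its external-rotation condition and add: *Between-group differences in SPADI, active flexion and active external rotation at 3 months will be estimated with adjustment for the baseline value of the same measure (ANCOVA) and reported with 95% CIs. The 10-degree benchmark applies to the adjusted flexion difference, which will be presented with its CI.*

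In Section 6.5, replace "any potential signal of efficacy due to improvement in range of shoulder motion as a result of anti-TNF injection" with: *the baseline-adjusted differences in SPADI and range of shoulder motion at 3 months, with their 95% CIs*.

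Add no pass or fail rule based on the interval. Requiring it to exclude zero would fail often even with a true 10-degree benefit: at r = 0.7 it would exclude zero in 84%, 50% and 31% of trials at SD 20, 30 and 40. Counting an interval wholly below 10 degrees against progression would sit badly with the statement in 6.3 that "Even small increases in range of shoulder motion are important to people with frozen shoulder".

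The cost is wording in two places and one baseline term per model. No new data, visits or participants are needed.
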